5.8.1. Disbursement and First Administration of Pre-Surgical Medications

Following the completion of all assessments, the patients will receive their pre-surgical antiinflammatory and antibiotic medications: PRED FORTE, PROLENSA, and VIGAMOX. The

87

medications will be administered by the patients on Day 26, 27, and 28 twice a day for each medication, once in the morning and once in the evening. Following the removal of the ENV515 implant (Visit 9/Day 28), it is upon the discretion of the investigator to determine the post-operative medication regimen. Patients will be provided with instructions on use of these medications and what to do to prepare for their cataract surgery.

Patients are expected to remain in the clinic for the completion of all procedures (~8:00 a.m. to ~4:30 p.m.). However, at the discretion of the investigator, patients will be permitted to leave the clinic after completing the 10:00 a.m. IOP measurement and will return to the clinic before the 4:00 p.m. IOP measurement. Any patient that leaves the clinic will be instructed to return no later than 30 minutes prior to 4:00 p.m. Before patients leave the clinic for the day, they should receive an appointment for their next study visit and the instructions provided in Section 5.1.2.

5.9. Visit 9/Day 28/Cataract Surgery, Cohort 1

Query patient about changes in concomitant medications and whether or not they have experienced symptoms suggesting an AE. AEs will be documented.

5.9.1. Pre-surgery Assessment, Cohort 1

Assessments will be conducted in the following order. Both eyes will be evaluated at all ophthalmic assessments:

- 1. Assess BCVA (ETDRS) with manifest refraction
- 2. If dilation is required to properly conduct BCVA (ETDRS) with manifest refraction the assessment should be performed after the slit lamp biomicroscopy and IOP measurement.
- 3. Perform slit lamp biomicroscopy
- 4. Perform corneal staining
- 5. Measure IOP at 8:00 a.m. (±30 minutes)
- 6. Perform gonioscopy to identify the location of the ENV515 implants to facilitate implant recovery during the cataract removal procedure
- 7. Additional assessment needed prior to cataract removal conducted per discretion of the principal investigator

5.9.2. Cataract Removal Procedure Combined with Aqueous Humor Sampling and Implant Recovery, Cohort 1

Patients will be queried about changes in medications and whether or not they have experienced symptoms suggesting an AE. AEs will be documented. Any observations associated with a standard cataract extraction followed by intraocular lens implantation as conducted by the principal investigator per established protocols, such as expected levels of aqueous cells or flare, will be recorded as AEs.

Assessments will be conducted in the following order. Both eyes will be evaluated at all ophthalmic assessments:

- 1. Assess BCVA (ETDRS) with manifest refraction
 - If dilation is required to properly conduct BCVA (ETDRS) with manifest refraction the assessment should be performed after the slit lamp biomicroscopy and IOP measurement.
- 2. Perform pupil measurement

- 3. Perform slit lamp biomicroscopy
- 4. Perform corneal staining
- 5. Measure IOP at 8:00 a.m. (±30 minutes)
- 6. Perform gonioscopy
- 7. Perform pachymetry (contact)
- 8 Assess VF
- 9. Perform anterior chamber OCT
- 10. Perform dilated funduscopic exam
- 11. Perform physical examination (can be performed anytime during the site visit and does not need to follow the order as written)
- 12. Assess vital signs (can be performed anytime during the site visit and does not need to follow the order as written)
- 13. Collect non-fasting blood and urine for clinical laboratory tests and systemic PK
- 14. If female of childbearing potential, perform urine or serum pregnancy test

Patients are expected to remain in the clinic for the completion of all procedures (\sim 8:00 a.m. to \sim 10:00 a.m.). Before patients leave the clinic, they should receive an appointment for their next study visit and the instructions provided in Section 5.3.4.

5.11. Visit 11/Day 42 to 49/Study Exit, Cohort 1

Query patient about changes in concomitant medications and whether or not they have experienced symptoms suggesting an AE. AEs will be documented. Any observations associated with a standard cataract extraction followed by intraocular lens implantation as conducted by the principal investigator per established protocols, such as expected levels of aqueous cells or flare, will be recorded as AEs.

Assessments will be conducted in the following order. Both eyes will be evaluated at all ophthalmic assessments:

- 1. Assess BCVA (ETDRS) with manifest refraction
 - If dilation is required to properly conduct BCVA (ETDRS) with manifest refraction the assessment should be performed after the slit lamp biomicroscopy and IOP measurement.
- 2. Perform slit lamp biomicroscopy
- 3. Perform corneal staining
- 4. Measure IOP at 8:00 a.m. (±30 minutes)

- 5. Perform specular microscopy (non-contact)
 - Non-contact specular microscopy can be performed anytime during the site visit and does not need to follow the order as written.
- 6. Complete the exit form
- 7. Discharge the patient from the trial

Patients are expected to remain in the clinic for the completion of all procedures (\sim 8:00 a.m. to \sim 10:00 a.m.). The patient will exit the trial barring any clinically significant, possibly related or related unresolved AEs.

5.12. Unscheduled Visits, Cohort 1

Patients may need to be seen at other times than the scheduled study visits for additional safety assessments or to follow-up, as medically necessary, on changes in clinical status or to follow-up on clinical laboratory or other findings. If an additional study visit occurs, the date and nature of the visit will be documented.

During unscheduled visits, query patient about changes in concomitant medications and whether or not they have experienced symptoms suggesting an AE. AEs will be documented.

Assessments will be conducted in the following order. Only study eye will be evaluated at the listed ophthalmic assessments, with additional evaluations carried out as deemed necessary per the investigator's discretion:

- 1. Assess BCVA (ETDRS) with manifest refraction
 - If dilation is required to properly conduct BCVA (ETDRS) with manifest refraction the assessment should be performed after the slit lamp biomicroscopy and IOP measurement.
- 2. Measure IOP at 8:00 a.m. (±30 minutes) or when feasible

6. TREATMENT OF PATIENTS, COHORT 1

6.1. Treatments to be Administered, Cohort 1

6.1.1. Implantation of ENV515, Cohort 1

Treatment consisted of a single intracameral injection of ENV515 (travoprost) Intracameral Implant(s) into a pre-surgical eye that was scheduled for cataract removal. A single drop of TRAVATAN Z was administered into the non-study eye as indicated daily from Visit 3 (Day 1) to Day 24, one day prior to Visit 8 (Day 25 ± 1 day). TRAVATAN Z was collected from the patients during Visit 8 (Day $25, \pm 1$ day).

At the randomization/treatment visit (Visit 3), patient's pre-surgical eye was assigned to 1 of the dose levels of ENV515 and patients received 1 to 3 ENV515 (travoprost) Intracameral Implant(s) into the pre-surgical eye via intracameral injection administered via the provided intracameral implant applicator. All investigators were trained in implant loading, administration and retrieval by Envisia. The site received randomization information based on randomization schedule following Visit 2 specifying which ENV515 formulation (ENV515-1 or ENV515-3) and how many implants to administer. The randomization code for this open-label study was computer-generated. To randomize a patient (Visit 3), the investigator (or designee) confirmed in the eCRF that the patient remains qualified for the study. The eCRF automatically assigned the dose and number of implants that the patient was to receive based on a prospectively prepared computer generated code list.

The study treatment assignment of 1 of 4 dose levels of ENV515 to be administered was determined by the randomization code. ENV515-1 and ENV515-3 (travoprost) Intracameral Implant(s) were supplied in sterile glass vials with 1 implant per vial. The sterile implant applicator was provided in a Tyvek® pouch. The packages were opened and the implant applicator and the implants were placed into a sterile field. The implants were loaded into the implant applicator by the investigator immediately prior to dosing. The implant size (ENV515-1 or ENV515-3) and the number of implants to load into the implant applicator was determined based on the randomization code identifying 1 of 4 dose levels described in Section 3.2.1. Additionally, the study eye was administered topical antibiotic VIGAMOX following the completion of the pre-dose assessments (Section 5.3.1) and immediately before and after the ENV515 implant administration as described below. The following instructions were distributed with the ENV515 implants and implant applicator:

Opening Instructions, Cohort 1

- 1. Use sterile technique in sterile field to open primary packaging for the applicator and ENV515 implants.
- 2. Open ENV515 Phase 2a Implant Applicator packaging and place the sterile ENV515 applicator into sterile field.
- 3. Do not open glass vial containing implants until ready to load into the applicator.

Instructions for Loading the Implant into the Applicator by the Principal Investigator, Cohort 1

1. Load ENV515 implant(s) into the ENV515 Phase 2a implant applicator in a sterile field using sterile technique via insertion through the beveled needle end. The implant type (ENV515-1 or ENV515-3) and the number of implants will be specified in the randomization code.

Instructions for Administration by Principal Investigator, Cohort 1

- 1. Treat subject's ocular surface with topical anesthetic (proparacaine 0.5% or equivalent).
- 2. Treat subject's ocular surface, periocular skin, eyelid margins and eyelashes with povidone iodine and wait 2 minutes.
- 3. Insert lid speculum.
- 4. Instill one drop of VIGAMOX into the study eye.
- 5. Administer the implant(s) into the anterior chamber via intracameral injection through clear, peripheral cornea. The needle should be advanced parallel with the iris, ~1 mm anterior to the limbus with the subject sitting at the slit lamp, or with the subject supine under the operating scope.
- 6. Instill one drop of VIGAMOX into the study eye.

One implant applicator and 5 glass vials with one ENV515-1 or ENV515-3 implant/vial will be packaged in an appropriately labeled carton. The label on the package will minimally contain the following information: each package contains no less than 5 glass vials with either one ENV515-1 or ENV515-3 implant/vial and one ENV515 implant applicator; study ENV515-01, storage temperature, and "Caution: Limited by Federal (or United States) Law to Investigational use". An unmasked disclosure panel will be displayed on the bottle label of the study medication and will minimally contain the following information: ENV515-01, and name of product. The study medications will be stored in a secure area with limited access to study personnel under refrigerated storage at approximately 2 to 8°C.

6.1.2. TRAVATAN Z for Non-Study Eye, Cohort 1

TRAVATAN Z will be provided for the non-study eye with its original packaging, labeling, and instructions for use (non-study eye only).

7. ASSESSMENT OF EFFICACY, COHORT 1

Assessments of efficacy included:

• IOP measurements completed at all visits. A diurnal curve of IOP measurements will be completed on Visit 2/Baseline and Visit 8/Treatment Day 25.

The IOP assessments and their timing are outlined in Table 1 and Section 5.

8. ASSESSMENT OF SAFETY, COHORT 1

8.1. Safety Parameters, Cohort 1

Safety and tolerability of ENV515 were evaluated using the following assessments:

- Specular microscopy (non-contact)
- Slit-lamp biomicroscopy
- Corneal staining
- Dilated fundus examination
- Gonioscopy exam
- Anterior chamber OCT exam
- Pupil measurement
- Pachymetry (contact)
- BCVA
- VF
- Physical examination
- Vital signs
- Non fasting clinical laboratory tests (chemistry and hematology)
- Serum or urine pregnancy tests for females of childbearing potential
- AEs

These assessments and their timing are outlined in Table 1 (Cohort 1 Time and Events Schedule) and Section 5. Compliance with study drug administration was also be assessed (Section 16.3).

Connecticial

9. TRIAL OBJECTIVES AND PURPOSE, COHORTS 2 AND 3

The primary objective of the Cohort 2 and 3 phases of this study is to:

• Evaluate in a dose escalating design the long-term safety and tolerability of a single, unilateral low dose of two ENV515-3 (travoprost) intracameral implants/eye in Cohort 2; and low and high doses of one and two ENV515-3-2 (travoprost) intracameral implants/eye, respectively, in Cohort 3 in patients with bilateral ocular hypertension or primary open-angle glaucoma; and

10. TRIAL DESIGN, COHORTS 2 AND 3

Cohorts 2 (5 patients) and 3 (15patients) are 12-month, prospective, open-label, activecomparator-controlled, multicenter, dose escalating cohorts of this Phase 2a trial. Cohort 2 had a 6-month optional Extension 1 followed by an additional 3-month optional Extension 2 (for up to a total of 21 months), increasing the total study duration to approximately 23 months. Cohort 3 has a 6-month optional Extension 1 followed by an additional 6-month optional Extension 2 (for a total of 24 months), increasing the total study duration to approximately 26 months. Cohorts 2 and 3 were designed to assess the long-term safety, tolerability, and systemic exposure to travoprost after a single low dose (ENV515-3) in Cohort 2; and single low or high doses of (ENV515-3-2) in Cohort 3 in patients with bilateral open-angle glaucoma or ocular hypertension (see inclusion criteria in Section 11.1). For the purposes of the Cohorts 2 and 3, patients are eligible if in the opinion of the investigator they have an IOP in both eves that is considered to be adequately controlled at the screening visit, can be safely withdrawn from IOP medications in both eyes during the washout period, and are not considered to be at significant risk for disease progression throughout the trial. The dose levels of travoprost in Cohorts 2 and 3 of this study are achieved by administration of a single, unilateral intracameral injection of each formulation with 28.2 µg travoprost/eye in Cohort 2; and 26.1 µg and 52.2 µg travoprost/eye in Cohort 3. These dose levels will be achieved via two implants per eye for low dose of ENV515-3 in Cohort 2; and one and two implants per eye for the low and high doses of ENV515-3-2, respectively, in Cohort 3. The study eye is prospectively defined as the eye with higher IOP or the left eye if IOP values are equal in both eyes on Dosing Visit (Day 1). All non-study eyes will receive openlabel timolol maleate 0.5% ophthalmic solution administered twice a day (Figure 4 and Figure 5).

Figure 4: ENV515 Treatment, Cohort 2

Treatments for the Study Eye vs. Non-Study, Fellow Eye

[figure not shown]
[figure not shown]

[figure not shown]
Figure 5: ENV515 Treatment, Cohort 3

Treatments for the Study Eye vs. Non-Study, Fellow Eye

On the Day 1 Dosing (Visit 3), low dose of ENV515-3 in Cohort 2, or low or high doses of ENV515-3-2 in Cohort 3 will be administered. Following Day 84 of the treatment phase (Dosing Visit 3/Day 1 to Treatment Visit 7/Day 84 [±7 days]), an analysis of IOP treatment effect as a change in mean diurnal IOP from mean diurnal IOP baseline will be conducted as the primary efficacy outcome measure. Following the completion of the rest of the study treatment period Month 4 (Visit 8) to Exit/Early Exit (Visit 16, Visit 22, or Visit 25) for the Cohort 2 alone, all safety and tolerability analyses will be conducted (Figure 6).

Figure 6: Study Design for ENV515-01 (Cohorts 2 and 3)

For Cohort 2, the study design included up to 26 clinic visits over approximately 23 months (12 months of Cohort 2, 6-month optional Extension 1, and 3-month optional Extension 2). For Cohort 3, the study design includes up to 28 clinic visits over approximately 26 months (12 months of Cohort 3,6-month optional Extension 1, and 6-month optional Extension 2). Following the Screening Visit, patients will be required to washout current glaucoma medication(s) (Section 16.1) for 4 weeks with up to an additional 2-week extension or 6 weeks

97 Version 19Feb2018

Communition

depending on Cohort. Patients will be required to return for an IOP baseline check during the Baseline Visit (Visit 2/Day -7 to -1) following the wash-out period. A single dose of ENV515-3 (two implants/eye) or ENV515-3-2 (one or two implant(s)/eye) will be given via intracameral injection during Dosing Visit 3/Day 1.

Patients will receive the following investigational product doses in the study eye on Day 1 Dosing (Visit 3) and will receive timolol maleate 0.5% ophthalmic solution to use in the non-study eye twice daily starting on the evening of Day 1 and continuing through the day prior to Month 12 (Visit 16), Month 18 (Visit 22), or Month 21 (Visit 25) for Cohort 2 or Month 24 (Visit 28) for Cohort 3.

- Cohort 2 low dose level: two implants/eye of ENV515-3 (28.2 μg/eye)
- Cohort 3 low and high dose levels:
 - one implant/eye of ENV515-3-2 (26.1 μg/eye)
 - two implants/eye of ENV515-3-2 (52.2 μg/eye)

Diurnal IOP curves will be measured at select study visits with the exception of the abbreviated visits at the Screening Visit (Days -49 to -42 for Cohort 2 and Days -56 to -42 for Cohort 3) Dosing Visit 3 (Day 1), Treatment Visit 4 (Day 2), and Treatment Visit 5a (Day 28), and selected visits depending on the Cohort and Extension(s).

Throughout the study, patients will undergo multiple safety assessments. A schedule of assessments is outlined in the sections below and in Table 1, Table 2, Table 3, Table 4, Table 5, Table 6, and Table 7.

10.1. Safety Evaluations, Cohorts 2 and 3

10.1.1. Review of Safety Data by Medical Monitor, Cohorts 2 and 3

A review of unmasked ocular safety data from each patient will be performed on an ongoing basis by a medical monitor. All ocular safety data for each patient will be provided to the medical monitor as it is generated throughout the trial. A patient may be discontinued at any time during the study at the discretion of the medical monitor for reasons referenced in, but not limited to Section 15.2.1. In addition, a meeting with the Envisia project team may be requested by the medical monitor at any time during the study to conduct a full evaluation of safety, which may result in a recommendation to terminate the study.

10.2. Safety Endpoints, Cohorts 2 and 3

The safety endpoints of the Cohorts 2 and 3 phases of this study are:

- Incidence of AEs;
- Changes in ophthalmic examination parameters (slit-lamp biomicroscopy, corneal staining, dilated funduscopic exam, anterior segment photos, pupil measurement,

using program 24-2);

Confidential

ocular symptom questionnaire, and VF as measured by the Humphrey Field Analyzer

- Changes in endothelial cell count and endothelial cell morphology using specular microscopy;
- Changes in corneal thickness as measured using pachymetry;
- Changes in IOP, including diurnal curve, as measured using a Goldmann applanation tonometer;
- Changes in BCVA with manifest refraction using the ETDRS chart;
- Changes in body systems assessment, vital signs, and laboratory parameters;
- Rate of discontinuation from the study; and
- Drug levels (travoprost free acid) in plasma.

10.3. Endpoints, Cohorts 2 and 3

10.3.1. Trial Treatments, Cohorts 2 and 3

The single low dose of 28.2 μ g travoprost/eye will be achieved via two ENV515-3 implants/eye in Cohort 2. Single low and high doses of 26.1 and 52.2 μ g/eye travoprost will be achieved via one or two ENV515-3-2 implants/eye, respectively, in Cohort 3 dosed into the study eye, with the non-study eye receiving timolol maleate 0.5% ophthalmic solution dosed twice a day.

10.3.2. Study Eye Selection

The central reading centers will determine eligibility of one or both eyes based on inclusion criteria related to corneal endothelial cell counts and anterior chamber angles assessed at Screening (Visit 1). At least one of the eyes must meet both inclusion criteria of cell counts and angle in addition to the other eligibility criteria. If both eyes are eligible, the study eye is defined as the eye with the higher mean diurnal IOP at Baseline (Visit 2) or the left eye if the mean diurnal IOP values are equal for both eyes at Baseline (Visit 2).

10.4. Methods to Minimize Bias in Cohorts 2 and 3

Patients were prospectively assigned to one dose of ENV515-3 in Cohort 2. In Cohort 3 ENV515-3-2 will be administered into the study eye, starting with the high dose level first (n=9) and proceeding to the low dose (n=6). The study eye is prospectively assigned based on predefined criteria (Section 11.3 and Section 11.4). The non-study eye will receive timolol maleate 0.5% ophthalmic solution. The patients, investigators, site staff, and project teams at Envisia, and the medical monitor, will be unmasked to treatment assignment.

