- 21. Patients who, per investigator's judgment, are not good clinical trial candidates due to personal (e.g., perceived willingness or ability to comply with protocol, significant traveling distance to medical center) and/or medical (e.g., mental illness, other non-ocular medical conditions, or laboratory abnormalities that might negatively impact trial participation or outcome) conditions that would likely impede the patient's successful study completion or planned analyses.

Response Measures:

Primary Efficacy Measure:

• Change from baseline in time-matched IOP measurements at Week 2, Week 6, and Week 12 (Day 14, 42, and 84) for study and non-study eye

Secondary Efficacy Measures:

- Change from baseline and percent change from baseline in time-matched IOP measurements for study eye and non-study at all other study time points and visits
- Difference in change from baseline and percent change from baseline in time-controlled IOP measurements between study eye and non-study eye at all study time points and visits
- Cumulative % of study and non-study eyes with at least 20, 25, and 30% reduction in IOP at all study time points and visits
- Cumulative % of patients with IOP <18 at all time points at each study visit
- Mean IOP at all visits all time points

Safety Measures: Assessed by evaluating changes from baseline in the following:

- Specular microscopy (non-contact)
- Slit-lamp biomicroscopy
- Corneal staining
- Dilated fundus examination
- Gonioscopy exam
- Anterior chamber OCT exam
- Pupil measurement
- Pachymetry (contact)
- BCVA
- Visual Field

- Body system assessment
- Vital signs
- Non fasting clinical laboratory tests (chemistry, hematology, and urinalysis)
- Urine pregnancy tests for females of childbearing potential
- AEs

Pharmacokinetic Measures:

• Systemic exposure to travoprost via analysis of travoprost acid in plasma

Study Extension 1 Synopsis, Table 3.

Confidential

Table 2: Time and Events Schedule, Cohort 2

Note: V16/Month 12 Time and Events Schedule should only be used if patients are not continuing into the Cohort 2 Study Extension 1 and plan to exit the study at V16/Month 12. If the patient is continuing into the Cohort 2 Study Extension 1, V16/Month 12 should follow the Time and Events Schedule in the Cohort 2

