- 3. Measure IOP at 8:00 a.m. (±30 minutes) or when feasible
- 4. Perform pachymetry (contact)
- 5. Perform specular microscopy (non-contact), can be performed anytime during the site visit
- 6. Adverse Event assessment
- 7. Concomitant medication assessment

14. TREATMENT OF PATIENTS, COHORTS 2 AND 3

14.1. Treatments to be Administered, Cohorts 2 and 3

14.1.1. Implantation of ENV515, Cohorts 2 and 3

Treatment will consist of a single intracameral injection of low dose ENV515-3 (travoprost) Intracameral Implants in Cohort 2, and a single intracameral injection of low or high dose of ENV515-3-2 (travoprost) Intracameral Implants in Cohort 3 into the study eye, defined as the qualifying eye with higher mean diurnal IOP during the Baseline Visit or the left eye if both eyes have the same mean diurnal IOPs at the Baseline Visit. The study eye will be selected during the Dosing Visit (Visit 3). All investigators will be trained in implant loading, administration, and retrieval (if necessary) by Envisia. Timolol maleate 0.5% ophthalmic solution will be administered into the non-study eye once on Day 1 at 8:00 p.m. Starting on Day 2 patients will administer timolol maleate 0.5% ophthalmic solution twice a day (8 a.m. and 8 p.m. ± 60 minutes) until the night prior to Visit 16 (Month 12) in the non-study eye.

ENV515-3 and ENV515-3-2 (travoprost) Intracameral Implants will be supplied in sterile glass vials with 1 implant per vial. The sterile implant applicator will be provided in a Tyvek® pouch. The packaging will be opened and the implant applicator and the implants will be placed into a sterile field. Implants will be loaded into the implant applicator by the trained investigator or trained Envisia staff member immediately prior to dosing. Additionally, the study eye will be administered 3 doses of topical antibiotic VIGAMOX: first dose following the completion of the pre-dose assessments (Section 12.3.1 and Section 13.3.1) and immediately before and after the ENV515 implant administration as described below. The following instructions will be minimally distributed with the ENV515 implants and implant applicator:

Opening Instructions, Cohorts 2 and 3

- 1. Use sterile technique in sterile field to open primary packaging for the applicator and ENV515 implants.
- 2. Open ENV515 Implant Applicator packaging and place the sterile ENV515 applicator into sterile field.
- 3. Do not open glass vial containing implants until ready to load into the applicator.

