8. EFFICACY EVALUATION

8.1 Primary Efficacy Analysis

The primary efficacy endpoint for this study is the change from baseline in time-matched IOP measurements for the study and non-study eye. Intraocular pressure is collected at 8 am. Values for IOP and change from baseline will be summarized by visit and time, cohort dose group, and eye as specified in Section 3. Baseline will be defined as the last IOP measurement prior to implantation and will be time-matched. No formal statistical testing will be done.

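### Cohorts 2 and 3: where the visit that picks the study eye on higher IOP is also the baseline for change, regression to the mean favours ENV515 over timolol, and the documents disagree on which visit does each job

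*Protocol*

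**What the plan says.** **Which eye gets the implant.** Protocol 10.3.2 states the rule as "If both eyes are eligible, the study eye is defined as the eye with the higher mean diurnal IOP at Baseline (Visit 2"), with the left eye on a tie. Protocol 14.1.1 repeats it ("qualifying eye with higher mean diurnal IOP during the Baseline Visit"), and so does 18.1. Protocol Section 10 (Trial Design, Cohorts 2 and 3) and the Cohorts 2/3 SAP 2.2 give a different visit: the eye with the higher IOP, or "the left eye if IOP values are equal in both eyes on Dosing Visit (Day 1"). Under 10.3.2, IOP decides only when both eyes meet the cell-count and angle criteria.

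**What change is measured from.** Protocol Section 10 says "an analysis of IOP treatment effect as a change in mean diurnal IOP from mean diurnal IOP baseline will be conducted". A full diurnal curve before dosing exists only at Visit 2, because Day 1 has one morning reading (Tables 2 and 5, footnotes; Sections 12.3.1 and 13.3.1). SAP 8.1 says instead "Baseline will be defined as the last IOP measurement prior to implantation and will be time-matched". It mentions collection at 8 a.m. only, but it summarises by visit and time, and Table 14.2.1 is by time point.

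**What is compared.** The Cohort 2 hypothesis is numerical comparability with the timolol eye, with no margin. The Cohort 2 synopsis lists "Difference in change from baseline and percent change from baseline in time-controlled IOP measurements between study eye and non-study eye" as a secondary measure, and SAP Section 10 drops summaries of secondary endpoints. What remains is SAP 8.1: "Values for IOP and change from baseline will be summarized by visit and time, cohort dose group, and eye", with no testing. Cohort 3 has no efficacy hypothesis.

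**How the rule is presented.** Section 10.4, on minimising bias, says "The study eye is prospectively assigned based on predefined criteria". It points to Sections 11.3 and 11.4, which contain no rule for choosing the eye.

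**The concern.** The higher of two noisy readings is, on average, high partly through error. At the next visit that part disappears: the chosen eye falls and the fellow eye rises relative to it, whatever the treatment. If change is measured from the same reading, the fall is credited to ENV515.

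At stake is a table with change columns for ENV515 and timolol side by side, read against a hypothesis of numerical comparability. The table carries no paired difference, no baseline adjustment and no warning that the two columns were sorted on baseline. More patients would not remove a tilt of this kind. Cohort 1 is free of it, because its study eye was the one scheduled for cataract surgery.

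**Working it through.** The plan gives no figure for this comparison, so there is none to reproduce.

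**Inputs from the documents.** The two selection rules and two reference definitions above. Entry limits at Visit 2: 22–34 mmHg at 8 and 10 a.m., 19–30 mmHg at 4 p.m., eyes within 4 mmHg at each time. Entry limits on Day 1: 22–34 mmHg, eyes within 4 mmHg.

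**Assumed inputs, not in the documents.** SD of the true between-eye difference, τ: 0.5–2.5 mmHg. Eye-specific visit SD, v: 0.5–1.2. SD of a single-time reading, m: 0.7–1.2.

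**Closed form, ignoring entry limits.** Let s be the SD of the visit error in the between-eye difference.

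- Diurnal mean of three times: s² = 2(v² + m²/3).
- Single reading: s² = 2(v² + m²).
- Spurious advantage in change when selection and reference coincide: √(2/π) · s² / √(τ² + s²).
- Remaining absolute difference at follow-up (study eye higher): √(2/π) · τ² / √(τ² + s²).

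**Worked case, τ = 1, v = 0.7, m = 1.0.**

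- Visit 2 diurnal: s² = 2(0.49 + 0.333) = 1.65, s = 1.28. Advantage = 0.798 × 1.64 / √2.64 = 0.80 mmHg. Residual absolute difference = 0.798 × 1 / √2.64 = 0.49 mmHg. With the entry limits simulated, these become 0.67 and 0.38.
- Day 1 single reading: s² = 2(0.49 + 1.0) = 2.98, s = 1.73. Advantage = 0.798 × 2.98 / √3.98 = 1.19 mmHg; simulated with limits, about 1.1.

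Under Visit 2 selection, the error at any one Visit 2 time has covariance 2(v² + m²/3) with the error in the selecting mean. The expected tilt is therefore the same at 8 a.m., 10 a.m., 4 p.m. and for the mean.

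**Simulation** (400,000 patients per setting, both eyes eligible, equal treatment effect in both eyes, all limits above). Positive values favour ENV515:

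| Selection | Reference for change | Spurious difference, mmHg |
|---|---|---|
| Visit 2 diurnal mean | Visit 2: diurnal mean or any single time | 0.2 to 1.1 |
| Visit 2 diurnal mean | Day 1, 8 a.m. | −0.29 to −0.01 |
| Day 1 | Day 1, 8 a.m. | 0.5 to 1.5 |
| Day 1 | Visit 2 diurnal mean | −0.35 to −0.01 |

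The small negative values come from the entry limits at the visit used as reference. In the Visit 2 runs, the absolute follow-up difference errs against ENV515 by about 0.1 to 1.1 mmHg.

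**Applied to the text.** Under 10.3.2, the tilt enters mean diurnal, 10 a.m. and 4 p.m. change, for which Visit 2 is the only possible reference. The 8 a.m. change escapes if the Day 1 reading is the baseline. That reading may be taken from 6 to 10 a.m. (±30 minutes); if it is not accepted as time-matched, the 8 a.m. reference reverts to Visit 2 and the tilt returns. Under SAP 2.2, selection is on Day 1 and the tilt moves to 8 a.m. Neither rule clears every time point.

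**The case against.** The strongest reply is that the SAP's literal baseline is the last reading before implantation, and the only time it names is 8 a.m. With eyes chosen on Visit 2 and a Day 1 reference, ENV515 gains nothing. That is right for 8 a.m. It does not cover 10 a.m., 4 p.m. or mean diurnal change, and it fails if the SAP's own Day 1 selection rule was followed.

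The variances are assumed. This stands. Cohort 1 reports SDs of change of 1.7 to 2.1 mmHg for the ENV515-3 and TRAVATAN Z groups, but these include differences in response and only bound the visit error from above.

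The consequence is limited. This also stands: Cohort 2 has five patients, the comparison is descriptive, and the report is abbreviated because the IND is being withdrawn. With an assumed paired SD of 1.8–2.5 mmHg, the standard error at n=5 is 1.8/√5 = 0.80 to 2.5/√5 = 1.12 mmHg, about as large as most of the tilt.

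SAP 8.1 already tabulates absolute IOP by eye. True, but it gives no paired difference and no guidance on reading the two together. A predefined rule does limit investigator choice in an unmasked study, but that is a different bias from the one described here.

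**Conclusion.** The point holds conditionally. Where the visit that chooses the eye is also the baseline, the side-by-side change favours ENV515 with no treatment difference: about 0.2 to 1.1 mmHg under Visit 2 selection and about 0.5 to 1.5 mmHg at 8 a.m. under Day 1 selection. Where the visits differ, the error is near zero or slightly against ENV515. These sizes rest on assumed between-eye and visit-to-visit variances, and on IOP having chosen the eye.

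A reader might infer that every change from baseline in the SAP is tilted, or that the tilt has one known size. The documents support neither: the selection and reference visits are each stated in two ways, and no variance is given. A reader might also carry the point over to a Cohort 3 efficacy claim. Cohort 3 makes none, so the practical weight falls on Cohort 2's comparability hypothesis.

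**What to change.** 1. Reconcile the selection visit (Protocol Section 10 and SAP 2.2 against Protocol 10.3.2, 14.1.1 and 18.1), and record which rule was applied. State in SAP 8.1 which visit is the baseline for each time point. Base the between-eye reading on a visit not used for selection where one exists: for example, a Day 1 reading taken at about 8 a.m. if eyes were chosen on Visit 2.
2. Where selection and baseline coincide, add to Table 14.2.1 the within-patient study-minus-fellow difference in absolute IOP at baseline and follow-up, beside the difference in change. Add a footnote giving the selection rule and stating that, in expectation, change errs for ENV515 and absolute IOP errs against it. Do not claim comparability from change alone.
3. Do not present the IOP-based eye rule in Section 10.4 as minimising bias for the ENV515–timolol comparison, and correct its cross-reference.

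Randomising the study eye is not proposed, because all 5 Cohort 2 and 15 Cohort 3 patients have been dosed. The cost is a few table rows from data already collected, one footnote, and a comparison that may look less favourable to ENV515.
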